8.3.4. NA Serum Antibody Responses

Descriptions of the NA assays and planned analyses will be described in an addendum to this SAP.

9. SAFETY EVALUATION

All summaries and analysis of safety data will be presented for the Safety Analysis Population. Safety summaries will be presented overall and grouped by study arm overall and by age stratum.

Continuous variables will be summarized using the following descriptive statistics: n (non-missing sample size), mean, standard deviation, median, maximum and minimum. All categorical measures will be summarized by the frequency and percentages of observed levels. The denominator for the percentages may be based on the number of non-missing observations for an assessment or based on the number of subjects in a population. This will be described for each table.

9.1. Demographic and Other Baseline Characteristics

Summaries of age, sex, ethnicity, race, BMI, and prior receipt of seasonal influenza vaccine will be presented by site in [Table 18](#) and [Table 19](#) and by study arm overall in [Table 20](#) and [Table 21](#). Age will be summarized as a continuous variable as well as by strata categories. Ethnicity is categorized as Hispanic or Latino, or not Hispanic and not Latino. In accordance with NIH reporting policy, subjects may self-designate as belonging to more than one race or may refuse to identify a race, the latter reflected in the electronic case report form (eCRF) as “No” to each racial option. BMI will be summarized as a continuous as well as categorical variable, categorized as (<30, ≥30). Self-reported history of prior receipt of seasonal influenza vaccine will be categorized as follows: 2017-2018, 2018-2019, receipt of none, or unknown. Demographic information for individual subjects will be provided in [Listing 6](#).

9.1.1. Prior and Concurrent Illnesses and Medical Conditions

All current illnesses and past or pre-existing medical conditions will be coded using Medical Dictionary for Regulatory Activities (MedDRA®) version 20.0 or higher.

Summaries of subjects’ prior and concurrent medical conditions will be presented by study arm in [Table 22](#).

Individual subject listings will be presented for all reported medical history including prior and concurrent medical conditions in [Listing 7](#).

9.1.2. Prior and Concurrent Medications

Concomitant medications will be coded to the Anatomical Therapeutic Classification using the WHO Drug Dictionary. The use of concomitant medications during the study will be summarized by ATC1 and ATC2 code and study arm for the Safety population in [Table 108](#). A listing of concomitant medications will be presented in [Listing 17](#).

9.2. Measurements of Treatment Compliance

All subjects are to receive 2 study vaccinations administered in the clinic. The number of study vaccinations administered to subjects will be presented by study arm and by site, overall in [Table 16](#) and [Table 17](#) and as part of the subject disposition in [Table 15](#).

[Listing 1](#) presents subjects who received investigational product with randomized study arm and study product received for each vaccination.

9.3. Adverse Events

A summary of all adverse events is provided in [Table 63](#). A summary of those events that occurred in $\geq 5\%$ of subjects in any treatment group is provided in [Table 64](#).

9.3.1. Solicited Events and Symptoms

Systemic solicited adverse events were collected pre-vaccination, and systemic and injection site solicited adverse events were collected at-least 20 minutes post-vaccination and then daily for 7 days after each vaccination and graded on a scale of 0 (absent), 1 (mild), 2 (moderate) and 3 (severe). Systemic events include fever, feverishness, fatigue, malaise, myalgia, arthralgia, headache, and nausea. The grading scale for systemic events, including quantitative grading for fever, is included in [Table 10](#). Injection site events include pruritus, ecchymosis, erythema, induration/swelling, pain, and tenderness. Ecchymosis, erythema, and induration are measured by both functional and measurement grading scales as defined in [Table 9](#).

When calculating the incidence of solicited events, each subject will be counted once at the highest severity following the applicable vaccination, and any repetitions will be ignored. For summaries presented separately for each vaccination, the denominator for percentages will be the number of subjects who received the respective vaccination with non-missing data for the event summarized. For summaries over all vaccinations the denominator will be the number of subjects who received at least one vaccination with non-missing data for the event summarized.

The number and percentage of subjects reporting at least one solicited adverse event of any severity will be summarized for each solicited symptom, any systemic symptom, any injection site symptom, and any symptoms. For each event the denominator is the number of subjects who received the applicable vaccination with non-missing data for the specific event. The 95% CI calculated using Clopper-Pearson methodology from a binomial distribution (SAS Proc Freq with a binomial option) will be presented in [Table 65](#), [Table 66](#), and [Table 67](#). Logistic regression models will be fit to estimate the effect of study arm on the probability of reporting any injection site event or reporting any systemic event in [Table 68](#) and [Table 69](#). If statistically significant effects are observed in the model for local events or systemic events, then additional models will be fit for each individual event of that type.

$$\text{logit}[P(\text{Event})] = \beta_0 + \beta_1 \times \text{Study Arm} + \varepsilon,$$

For each systemic and injection site event, any systemic event, any injection site event, and any solicited event, the maximum severity over 7 days after each vaccination will be summarized for the Safety population. The number and percentage of subjects reporting each event will be summarized by the maximum severity and treatment group overall and by age stratum, separately for each vaccination and over all vaccinations. For each event the denominator is the number of subjects who received the applicable vaccination with non-missing data for the specific event. The 95% CI calculated using Clopper-Pearson

methodology from a binomial distribution (SAS Proc Freq with a binomial option) will be presented in [Table 70](#), [Table 71](#), and [Table 72](#).

The number of subjects reporting a solicited adverse event will be summarized for each day post vaccination for each vaccination and for all vaccinations combined both as summary in [Table 73](#), [Table 74](#), and [Table 75](#) and graphically in a bar chart in [Figure 26](#) and [Figure 27](#). A comparison of the event rate for each treatment group between vaccination 1 and vaccination 2 will be presented, including p-values from McNemar's test performed over all subjects for injection site and systemic symptoms in [Table 76](#) and [Table 77](#).

Systemic and injection site solicited events reported by subject will be presented in [Listing 10](#) and [Listing 11](#), sorted by subject ID, vaccination number, parameter, and study day.

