10.5.2 Safety Data

Summaries and analysis of safety data will be presented for the Safety Analysis Population. All summaries and analyses will be presented for all subjects.

Solicited AEs will be summarized by severity for each day after each study vaccination (Days 1-7 post each study vaccination) and as the maximum severity over all 8 days. Additionally, solicited AEs will be analyzed by taking the most severe response over the follow-up period,

dichotomizing into a binary variable (none versus mild, moderate, or severe) and using standard techniques, such as exact confidence intervals, to summarize the proportion of subjects reporting each symptom, any injection site symptom, and any systemic symptom. Summaries of solicited AEs will be presented separately for each study vaccination as well as overall study vaccinations by treatment arm. The proportion of subjects reporting symptoms may be compared between treatment arms using Chi-square or Fisher's exact test. The proportion of subjects reporting solicited symptoms between the different study vaccinations (i.e., first and second) will be compared using McNemar's test.

Unsolicited AEs will be coded by Medical Dictionary for Regulatory Activities (MedDRA®) for preferred term and system organ class (SOC). The numbers of SAEs, MAAEs, including NOCMCs, and PIMMCs are likely to be small in this trial and will be reported by detailed listings showing the event description, MedDRA® preferred term and SOC, relevant dates (study vaccinations and AEs), severity, relatedness, and outcome for each event. Non-serious unsolicited AEs will be summarized as number and percentage of subjects reporting at least one event in each MedDRA® preferred term and SOC, cross tabulated by severity and relationship to study product. Additionally, the proportion of subjects and exact 95% confidence intervals of AEs in aggregate and by MedDRA® categories will be computed.

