14.3.1.1 Solicited Adverse Events

Table 65: Number and Percentage of Subjects Experiencing Solicited Events with 95% Confidence Intervals by Symptom and Study Arm – Post Any Study Vaccination - Safety Population

Symptom	Study Arm 1 3.75 mcg A/H7N9 + MF59 (N=X)		Study Arm 2 7.5 mcg A/H7N9 + MF59 (N=X)		Study Arm 3 15 mcg A/H7N9 + MF59 (N=X)		Study Arm 4 15 mcg A/H7N9 (N=X)	
	n	% (95% CI)	n	% (95% CI)	n	% (95% CI)	n	% (95% CI)
Any Symptom	x	xx (xx-xx)	x	xx (xx-xx)	x	xx (xx-xx)	x	xx (xx-xx)
Any Systemic Symptom								
Fever								
Feverishness								
Fatigue								
Malaise								
Myalgia								
Arthralgia								
Headache								
Nausea								
Any Injection Site Symptom								
Pain								
Tenderness								
Pruritus								
Ecchymosis								
Ecchymosis (measurement)								
Erythema								
Erythema (measurement)								
Induration/Swelling								

Table 65: Number and Percentage of Subjects Experiencing Solicited Events with 95% Confidence Intervals by Symptom and Study Arm – Post Any Study Vaccination - Safety Population (continued)

Symptom	Study Arm 1 3.75 mcg A/H7N9 + MF59 (N=X)		Study Arm 2 7.5 mcg A/H7N9 + MF59 (N=X)		Study Arm 3 15 mcg A/H7N9 + MF59 (N=X)		Study Arm 4 15 mcg A/H7N9 (N=X)	
	n	% (95% CI)	n	% (95% CI)	n	% (95% CI)	n	% (95% CI)
Induration/Swelling (measurement)								
Note: N = Number of subjects in the Safety population. 95% CI estimated using Clopper-Pearson exact method								

Tables with similar format:

Table 66: Number and Percentage of Subjects Experiencing Solicited Events with 95% Confidence Intervals by Symptom and Study arm – Post Study Vaccination 1 – Safety Population

[Footnote update] N = Number of subjects in the Safety population who received the first vaccination.

Table 67: Number and Percentage of Subjects Experiencing Solicited Events with 95% Confidence Intervals by Symptom and Study arm– Post Study Vaccination 2 – Safety Population

[Footnote update] N = Number of subjects in the Safety population who received the second vaccination.

Table 68: Logistic Regression Model to Evaluate the Relationship of HA Antigen Dose and MF59 Adjuvant with Reporting Any Injection Site Event - Post Any Study Vaccination – Safety Population

Model Parameter	Parameter Estimate		SE	p-value	Odds Ratio	95%CI
Intercept	xxx.x		xxx.x	x.xxx	-	-
Study Arm						
15 mcg with MF59 adjuvant (reference)	-		-	-	-	-
3.75 mcg with MF59 adjuvant	xxx.x		xxx.x	x.xxx	xx.x	xx.x-xx.x

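### The planned between-arm models of solicited reactions use any versus none, so the plan estimates no arm effect on severity

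*SAP*

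**What the plan says.** Protocol 8.1 and SAP 4.5.1 say safety will be judged on both the frequency and the severity of events, solicited reactions included. Protocol 3.3.1 and SAP 3.2.1 make the occurrence of solicited reactions a primary safety endpoint. SAP 9.3.1 grades each symptom 0 (absent) to 3 (severe).

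- **Comparison between arms.** SAP 9.3.1: "Logistic regression models will be fit to estimate the effect of study arm on the probability of reporting any injection site event" or any systemic event (Tables 68 and 69, over both doses). If these show a statistically significant effect, "then additional models will be fit for each individual event of that type", with the same logit of P(Event).
- **The cut.** Protocol 10.5.2 takes the worst response and describes "dichotomizing into a binary variable (none versus mild, moderate, or severe". It adds that the proportion reporting symptoms "may be compared between treatment arms using Chi-square or Fisher's exact test", which is optional and also binary.
- **Severity.** SAP 9.3.1: "the maximum severity over 7 days after each vaccination will be summarized for the Safety population", and "The number and percentage of subjects reporting each event will be summarized by the maximum severity and treatment group overall". Tables 70-72 carry exact intervals for each arm. Tables 73-75 and Figures 26-27 show severity by day. None of these contrasts the arms.
- **McNemar's test** compares dose 1 with dose 2 within an arm.

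**The concern.** Table 68 is titled "Logistic Regression Model to Evaluate the Relationship of HA Antigen Dose and MF59 Adjuvant with Reporting Any Injection Site Event". Its outcome is a composite of six symptoms, at any grade, over two doses. Its reference arm is 15 mcg + MF59, so two of its three contrasts compare adjuvanted arms. Two things follow.

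First, an any/none outcome carries no information on how bad the reactions are. If a higher antigen dose or MF59 turned mild reactions into moderate ones without changing how many people react, the odds ratio would stay at 1.

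Second, if most recipients report at least something, the any/none split is lopsided and says little about the arms. Because the per-symptom models depend on a significant any-event result, an effect missed there also removes the symptom-level estimates.

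**Working it through.** **Nearest figure in the plan.** No power is stated for these models. Protocol Table 10 gives detectable differences for a binary comparison of two adjuvanted arms (N = 100 each, 80% power, two-sided likelihood ratio test, alpha 0.05). Recomputed: 0.1975, 0.195, 0.1825, 0.1625, 0.1325 and 0.0875 for comparator rates 0.40 to 0.90. Rounded up, these match the protocol's 0.20, 0.20, 0.19, 0.17, 0.14 and 0.09. SAP Table 6 prints 0.29 at 0.50, where power would be 99%; the protocol's 0.20 is the one that reproduces.

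**Inputs.** From the documents: 106, 106, 106 and 53 per arm, grades 0-3. Assumed, because the documents give no rates: any-reaction rate 30-90% in the lower arm, reactors split 70/25/5 mild/moderate/severe, a common odds ratio (OR) of 2, two-sided 5% test.

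**Formulas.** A cumulative probability c in the lower arm becomes c' = 2c/(1 + c) in the other. With difference d and pooled and unpooled standard errors s0 and s1:
- Any/none power = Φ((d − 1.96 s0)/s1).
- Ordinal power = Φ(ln 2 × √V − 1.96), where V = n1 n2 n/[3(n+1)²] × (1 − Σ p̄³) and p̄ is the mean probability of each grade.

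**Worked at 80%, 106 v 106.** Lower arm, grades 0-3: 0.20, 0.56, 0.20, 0.04. Its cumulative values 0.80, 0.24, 0.04 become 0.889, 0.387, 0.077.
- Any/none: d = 0.0889, s0 = 0.0498, s1 = 0.0494, so Φ(−0.18) = 43%.
- Ordinal: p̄ = 0.156, 0.531, 0.255, 0.058; V = 17.50 × 0.830 = 14.5; Φ(0.693 × 3.81 − 1.96) = 75%.

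**Simulation** (40,000 trials per row; score test for each binary cut, tie-corrected Wilcoxon for the grade), 106 v 106, power in %:

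| Any rate, lower to higher arm | Any/none | Grade 0-3 | Gain | Moderate-or-worse |
|---|---|---|---|---|
| 30 to 46 | 68.0 | 69.6 | 1.6 | 38 |
| 50 to 67 | 68.8 | 76.6 | 7.8 | 51 |
| 70 to 82 | 56.6 | 76.6 | 20.0 | 61 |
| 80 to 89 | 43.2 | 74.5 | 31.3 | 64 |
| 90 to 95 | 25.8 | 72.3 | 46.5 | 67 |

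For 53 v 106, any/none against grade: 53 v 59 at 50%, 43 v 59 at 70%, 34 v 57 at 80%.

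The OR that the any/none model needs for 80% power at 106 v 106 is about 2.2 at a 50% rate, 2.6 at 70%, 3.3 at 80% and 7.3 at 90%.

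**Severity-only shift.** Any rate 75% in both arms, moderate-or-worse 15% v 27%, 106 v 106. Any/none rejects 5%, which is alpha. The ordinal test has 24% and the moderate-or-worse cut 58%. Check on the last: (0.12 − 1.96 × 0.0559)/0.0553 = 0.19, or 57%.

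**Mild-only rise.** Any rate 70% to 85%, moderate-or-worse 15% in both arms. Any/none has about 76% and the ordinal test about 46%.

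**The case against.** The case for leaving the plan alone has real weight.

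- **The model matches the endpoint and the protocol.** The primary endpoint is occurrence, and Protocol 10.5.2 specifies the same cut. This stands: a reader might infer a departure from the protocol, and there is none.
- **Severity is already displayed.** Tables 70-75 and Figures 26-27 show it by arm, and Grade 3 reactions feed the halting criteria in Protocol 8.6.1. A reader might infer that the plan as a whole cannot see a severity shift. The documents do not support that: the gap is in the models, which leave the reader to compare separate per-arm intervals without an estimate of the contrast.
- **The study tests no formal hypothesis** (Protocol 10.1, SAP 6.8). That limits the weight of the power figures. But the SAP reports p-values from these models and uses significance to decide whether further models are fitted, and pure estimation of arm effects also needs a severity contrast.
- **High reaction rates are assumed.** This stands. At 30% the loss is negligible, and no rate is given for either composite. Protocol 2.3.1 expects MF59 to bring slightly more mild, transient reactions, a pattern in which any/none does better.
- **A fixed odds ratio flatters the contrast near the ceiling.** An OR of 2 from 90% is a rise of under 5 percentage points, so part of the low power reflects a small absolute difference.
- **A proportional-odds model is a weak remedy for a pure severity shift.** This stands: 24% against 58% for the moderate-or-worse cut.

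**Conclusion.** The point holds as a gap in the models, not as a contradiction or an error. The planned between-arm models give no arm effect on severity, although severity is half of the stated safety assessment, and they cannot detect a shift in severity at a constant any-reaction rate. That part does not depend on the reaction rate.

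The power loss does. At OR 2, a 70/25/5 split and 106 v 106 it runs from about 2 points at 30% to 31 at 80%. A reader might infer that the models are badly underpowered; without reaction rates in the documents, that cannot be concluded. Nor does any single replacement win everywhere: any/none is best if only mild reactions rise, moderate-or-worse is best for a pure severity shift, and the ordinal model is best for a common shift across grades. The improvement is worth making because it is cheap and purely additive.

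**What to change.** In SAP 9.3.1 keep the any/none models. For any injection site and any systemic reaction, add the following without a significance gate:

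1. A logistic model of moderate-or-worse versus less on study arm, with odds ratios and 95% confidence intervals.
2. As a supporting analysis, a proportional-odds model of maximum severity (0-3) on study arm, with the common odds ratio and 95% confidence interval.

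Use the reference arm of Tables 68-69. State that maximum injection-site severity is based on the functional grade, with the millimetre measurement reported separately. This needs saying because Protocol Table 4 labels the measurements small, medium and large, SAP Table 9 labels them Grades 1-3, and SAP 9.3.1 does not say which scale enters the composite maximum.

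The cost is SAP wording and two to four model tables, with no new data, visits or subjects. The downsides are the proportional-odds assumption in (2), and less power than any/none in both additions if only mild reactions increase, which is why the any/none models stay.

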9.3.2. Unsolicited Adverse Events

When calculating the incidence of unsolicited AEs (i.e., on a per subject basis), each subject will only be counted once at the highest severity and/or relationship, and any repetitions of AEs within a subject will be ignored; the denominator will be the total number of subjects in the safety population. All AEs reported will be included in the summaries and analyses.

The number and percentage of subjects reporting at least one unsolicited AE will be summarized by MedDRA system organ class and preferred term. A 95% CI will be presented for the percentage of subjects reporting any unsolicited AE (serious or non-serious) for each MedDRA system organ class and preferred term over all study vaccinations in [Table 78](#).

The following summaries for unsolicited AEs will be presented by MedDRA system organ class, preferred term, and study arm:

- Incidence of AEs by severity and relationship to study product in [Table 79](#);
- Incidence of non-serious, related AEs by severity in [Table 80](#);
- Incidence of AEs over time (Days 1-8, Days 9-22 post each study vaccination) in [Table 81](#);
- Incidence of non-serious, related AEs over time (Days 1-8, Days 9-22 post each study vaccination) in [Table 82](#) – note this table presents results for secondary safety endpoint, “Occurrence of study vaccine-related unsolicited non-serious AEs from the time of each study vaccination through approximately 21 days after each study vaccination”;
- Total frequency of AEs over time (Days 1-8, Days 9-22 post each study vaccination) in [Table 83](#);
- Subject listing of non-serious AEs of moderate or greater severity in [Table 87](#);
- Bar chart displaying total frequency of AEs by severity and MedDRA system organ class, Study arm, and Age Stratum in [Figure 28](#);

- Bar chart displaying incidence of AEs by severity and MedDRA system organ class, Study arm, and Age Stratum in [Figure 29](#);
- Bar chart displaying total frequency and incidence of AEs by relationship to study product and MedDRA system organ class and study arm in [Figure 30](#) and [Figure 31](#).

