8.6.2 Individual Halting Criteria

The second study vaccination will not be administered to a subject if any of the following criteria are met:

- Subject meets any criteria in [Section 5.2.1](#), Withdrawal from the Study or Discontinuation of the Study Product.
- Presence of signs or symptoms that could confound or confuse assessment of study vaccine reactogenicity. For subjects with injection site or systemic signs or symptoms, or with an acute illness, including an oral temperature greater than or equal to 100°F, the second study

vaccination should be postponed/deferred until signs, symptoms, or acute illness have resolved, or are improving as further specified below, and if within the acceptable protocol-specified window for that visit (Day 22+7) (note: Grade 1 vaccine related solicited AE are permitted, see below). No exceptions to the protocol-specified window will be made. **Note for afebrile, acute illness only:** If a subject is afebrile, his/her acute illness is nearly resolved with only minor residual symptoms remaining, this occurs within the acceptable protocol-specified window for that visit (Day 22+7), and, in the opinion of the site PI or appropriate sub-investigator, the residual symptoms will not interfere with the ability to assess safety parameters as required by the protocol, the subject may receive the second study vaccination without further approval from the DMID Medical Officer. No exceptions to the protocol-specified window will be made.

- Grade 3 solicited or unsolicited AE that is ongoing, whether or not it is improved or resolving.
- Any unresolved or continuing Grade 2 AE that has not decreased in severity to Grade 1 or less.
- An unresolved or continuing Grade 1 AE is permissible following the documented determination by the site PI or appropriate sub-investigator, that it would not render study vaccination unsafe or interfere with the evaluation of responses.
- Grade 3 solicited or unsolicited AE that occurs without alternative etiology in the 8 days following the first study vaccination.

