6.3. Analysis Populations

6.3.1. Safety Population

The Safety Analysis population includes all subjects who received at least one study vaccination.

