Note: N = Number of subjects in the Safety population. This table presents number and percentage of subjects.									
[1] For severity, a subject is counted once per preferred term and is summarized according to their highest severity.									

Table 81: Number and Percentage of Subjects Experiencing Unsolicited Adverse Events Within 21 Days Post Study Vaccination by MedDRA System Organ Class and Preferred Term, Day Post Vaccination, and Study Arm – Safety Population

MedDRA System Organ Class	MedDRA Preferred Term	Day 1-8 Post Vac 1		Day 9-22 Post Vac 1		Day 1-22 Post Vac 1		Day 1-8 Post Vac 2		Day 9-22 Post Vac 2		Day 1-22 Post Vac 2		Day 1-22 Post Any Vaccination	
		n	%	n	%	n	%	n	%	n	%	n	%	n	%
Study Arm 1: 3.75 mcg A/H7N9 + MF59, (N=X)															
All Subjects															
Any SOC	Any PT	x	xx	x	xx	x	xx	x	xx	x	xx	x	xx	x	xx
[SOC 1]	Any PT														
	[PT 1]														
	[PT 2]														
[SOC 2]	Any PT														
	[PT 1]														
	[PT 2]														
[Repeat for all study arms]															
Note: N = Number of subjects in the Safety Population. This table presents number and percentage of subjects. For each time period, a subject is only counted once per PT.															

Table 82: Number and Percentage of Subjects Experiencing Non-Serious, Related Unsolicited Adverse Events Within 21 Days Post Vaccination by MedDRA System Organ Class and Preferred Term, Study Vaccination, and Study Arm – Safety Population

MedDRA System Organ Class	MedDRA Preferred Term	Day 1-8 Post Vac 1		Day 9-22 Post Vac 1		Day 1-22 Post Vac 1		Day 1-8 Post Vac 2		Day 9-22 Post Vac 2		Day 1-22 Post Vac 2		Day 1-22 Post Any Vaccination	
		n	%	n	%	n	%	n	%	n	%	n	%	n	%
Study Arm 1: 3.75 mcg A/H7N9 + MF59 (N=X)															
All Subjects															
Any SOC	Any PT	x	xx	x	xx	x	xx	x	xx	x	xx	x	xx	x	xx
[SOC 1]	Any PT														
	[PT 1]														
	[PT 2]														
[SOC 2]	Any PT														
	[PT 1]														
	[PT 2]														
[Repeat for all study arms]															
Note: N = Number of subjects in the Safety population. This table presents number and percentage of subjects. For each time period, a subject is only counted once per PT.															

Table 83: Number of Unsolicited Adverse Events by MedDRA System Organ Class and Preferred Term, Day Post Vaccination, and Study Arm – Safety Population

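### Post-dose-2 unsolicited AE percentages in SAP Tables 81 and 82 are divided by the full Safety population, so they are understated by the share of subjects who never received dose 2 (minor)

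*SAP*

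**What the plan says.** SAP 9.3.2 gives one denominator rule for unsolicited AE incidence: "the denominator will be the total number of subjects in the safety population". SAP 6.3.1 defines that set: "The Safety Analysis population includes all subjects who received at least one study vaccination".

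The same section plans summaries by time since each vaccination. The shells for Tables 81 and 82 have three dose-2 columns with n and %, among them "Day 1-22 Post Vac 2". The Table 81 footnote begins "N = Number of subjects in the Safety Population. This table presents number and percentage of subjects. For each time period" and continues with the rule of counting a subject once per term. Table 82 uses the same N. Neither shell shows a number of dose-2 recipients. SAP 9.3.2 names Table 82 as the display for the secondary endpoint on related non-serious unsolicited AEs.

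The introduction to SAP 9 leaves the choice open: "The denominator for the percentages may be based on the number of non-missing observations for an assessment", or on the size of a population, with the choice to be stated table by table. For Tables 81 and 82 the only statement is the Safety population. Protocol 10.5.2 gives no different rule.

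For solicited events shown by vaccination, SAP 9.3.1 says that "the denominator for percentages will be the number of subjects who received the respective vaccination with non-missing data for the event summarized". The footnotes to Tables 67 and 72 and the note to Figure 26 follow that rule.

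**The concern.** A percentage labelled as following the second vaccination is naturally read as a rate among people who had that vaccination. Here some of those counted in the denominator may not have had it. The numerator is closed to them by definition, and data collection also narrows: under Protocol 6.4.1 (Visits 05 to 07), subjects discontinued from dose 2 have AE collection limited to SAEs, MAAEs, NOCMCs and PIMMCs. Table 82 counts non-serious related events, most of which would not be collected from them.

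Two things are at stake. The dose-2 columns of a secondary-endpoint display would be systematically low. One study report would also carry post-dose-2 percentages on two different bases, dose-2 recipients for solicited events and the Safety population for unsolicited ones, with no reason given for the difference.

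**Working it through.** The documents state no post-dose-2 AE percentage, so there is no planned figure to reproduce. The check is on the rule itself.

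**Inputs**
- Denominator and population: SAP 9.3.2, 6.3.1 and the Table 81 and 82 shells.
- Arm sizes: 106 per adjuvanted arm and 53 unadjuvanted (SAP 5).
- d, the fraction of the Safety population without dose 2: not given. The nearest figure is the 5% of subjects who may be excluded from the primary endpoint analysis (Protocol 10.2, SAP 5). That covers exclusions of any kind, so it is a proxy only. The range 2% to 15% is an assumption.
- True post-dose-2 incidence: not given. 10%, 20% and 30% are assumed.

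**Formula.** Let N be the Safety population in an arm, m the number given dose 2, r the number of those with an event, and d = 1 − m/N. Then

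displayed rate = r/N = (r/m) × (m/N) = (rate among recipients) × (1 − d).

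The relative understatement is exactly d, and its direction is fixed as soon as one vaccinated subject misses dose 2.

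**Displayed percentage, by d and true rate**

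| d | true 10% | true 20% | true 30% |
|---|---|---|---|
| 2% | 9.8 | 19.6 | 29.4 |
| 5% | 9.5 | 19.0 | 28.5 |
| 10% | 9.0 | 18.0 | 27.0 |
| 15% | 8.5 | 17.0 | 25.5 |

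The shift is 0.5 to 1.5 points at d = 5% and 0.2 to 4.5 points over the whole grid.

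**Example in whole subjects.** Take an arm of 106 in which 101 receive dose 2 (d = 5/106, about 5%) and 20 of them report an event. The SAP rule gives 20/106 = 18.9%. Recipients as denominator give 20/101 = 19.8%.

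**Between arms.** With equal true rates, the ratio of displayed rates is (1 − d₁)/(1 − d₂). At d = 5% in both arms and a true 20%, both show 19.0% and the spurious difference is 0. If d were 10% in an adjuvanted arm and 2% in the unadjuvanted arm (an illustration only), they would show 18.0% and 19.6%, a spurious −1.6 points. Reversing the two values of d gives +1.6. The documents support neither split.

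**What is not affected.** Everyone in the Safety population received dose 1, so the dose-1 columns are right. So are the any-vaccination columns and Tables 78 to 80, which cover all vaccinations together. Table 83 gives counts only.

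**The case against.** The best case against making much of this has four parts.

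**Size.** At the 5% proxy, any cell with a true rate below 10% moves by less than half a point. SAP 10 prints percentages as whole numbers, so many cells would look the same. This stands.

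**No inference depends on it.** Tables 81 and 82 carry no confidence intervals and no tests, and SAP 6.8 disclaims testing of any specific null hypothesis. Table 15 reports how many received vaccination 2 by arm, so a reader can recover the rate from the printed n. This also stands. It limits the severity but does not make the printed percentage correct.

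**The sections do not contradict each other.** SAP 9 allows different denominators, and 9.3.1 and 9.3.2 deal with different data. That is fair: the practice is inconsistent rather than the instructions contradictory.

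**The fix does not make arms comparable.** If dose 2 is withheld because of reactions, the recipients are a selected group. This is correct, and the fix should not be presented as a cure for it.

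Two stronger readings are tempting. A reader might infer that the rule hides an adjuvant effect, because Protocol 8.6.2 withholds dose 2 after a "Grade 3 solicited or unsolicited AE that occurs without alternative etiology in the 8 days following the first study vaccination" and adjuvant may raise reaction rates. Protocol 2.3.1, however, speaks only of a possibility of more AEs with adjuvant and says nothing of Grade 3 events. It describes most reactions to MF59-adjuvanted vaccine as no worse than moderate, and reports an overall unsolicited AE risk no higher than with non-MF59 vaccine. A higher d with adjuvant is therefore possible but not shown. A reader might also infer that a planned dose 1 versus dose 2 comparison is biased. The only such comparison is McNemar's test on solicited events (Tables 76 and 77), and the footnote to that shell already restricts it to subjects given both doses. For unsolicited AEs, the most that is affected is a comparison of columns by eye.

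**Conclusion.** The point holds and is minor. Followed as written, the SAP understates every dose-2 percentage in Tables 81 and 82 by the relative fraction d. The direction is certain if anyone misses dose 2. The size depends on a d that the documents do not give: about 1 point at a true 20% if the 5% proxy applies, and 0.4 to 3.0 points over the assumed 2% to 15%. Distortion between arms needs a difference in d, which the withholding criteria make possible but nothing in the documents establishes. It is worth correcting because Table 82 is a named secondary-endpoint display and the SAP already applies the better rule to solicited events.

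**What to change.** In SAP 9.3.2, state that percentages shown by vaccination use the Safety-population subjects who received that vaccination, and that percentages over all vaccinations use the full Safety population. In the Table 81 and 82 shells, show the number of dose-2 recipients over the dose-2 columns and amend the footnotes to match. The dose-1 columns do not change.

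Add a note that the dose-2 percentage describes subjects who went on to dose 2. It is conditional on that receipt and does not remove selection between arms, so it should be read alongside the number per arm who missed dose 2 (Table 15) and the reasons (Listing 2).

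The cost is one sentence in the SAP and header and footnote edits to two shells. No data collection, sample size or inferential analysis changes.
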